10.1 Sample Size Considerations

The objective of the study is to assess baseline brain activity and genetic markers and secondarily to measure neurological changes during Ketamine sessions. This is an open-label, observational study to determine the feasibility of these measurements. The intent is to enrol 36 participants which should have the precision needed to observe and compare EEG activity pre, during and post Ketamine administration.

10.2 Data Analysis

The information will be summarized using description statistics (mean, median, standard deviation, minimum, maximum) for quantitative variables (e.g., cheek swabs, EEG data), and counts and percentages for categorical variables (e.g., gender).

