CRA	Clinical Research Associate
CRF	Case Report Form
CYP2B6 gene	CYP2B6 gene encodes the Cytochrome P450 class of metabolic enzymes found mainly in the human liver. It metabolizes ketamine, controlling how fast ketamine is eliminated from the body.
DISC1 gene	Disrupted in Schizophrenia 1 genotype. Well established as a genetic risk factor across a spectrum of psychiatric disorders. DISC1 is highly expressed during critical brain development periods.
DSM-V	Diagnostic and Statistical Manual of Mental Disorders, 5 th Edition
EEG	Electroencephalogram
Electrode	Conductor through which electricity enters or leaves
Endophenotype	A quantitative biological trait that is reliable in reflecting the function of a discrete biological system and it is reasonably heritable. It is also known as an intermediate phenotype. It is more closely related to the root cause of a disease than a broad, clinical phenotype.

GCP	Good Clinical Practice. This is a standard for the design, conduct, performance, monitoring, auditing, recording, analyses, and reporting of clinical trials that provides assurance that the data and reported results are credible and accurate, and that the rights, integrity and confidentiality of trials participants are protected.
HAM-D	Hamilton Depression Rating Scale. Widely used clinician-administered depression assessment scale.
HIPAA	Health Insurance Portability and Accountability Act
HPA Axis	Hypothalamic-Pituitary-Adrenal axis – central stress response system
HTR2A gene	HTR2A serotonin gene influences the serotonin 5-HT2A receptor pathway
ICH	International Council for Harmonisation of Technical Requirements for Pharmaceuticals for Human Use. This is an international body that sets guidelines for clinical research.
ICMJE	International Committee of Medical Journal Editors. A group of general medical journal editors and representatives of selected related organizations working together to improve the quality of medical science and its reporting.
IRB	Institutional Review Board. This is an independent body constituted of medical, scientific, and non-scientific member whose responsibility is to ensure the protection of the rights, safety and well-being of human participants involved in a clinical trial. Also known as the ethics committee.
Ketamine	Belongs to a class of drugs known as dissociative anesthetics. It is a noncompetitive NMDAR antagonist.
MDD	Major Depressive Disorder

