1.2 Background

Ketamine traditionally has been used as an anesthetic. It is a NMDA receptor antagonist which has rapid and potent antidepressant effects in treatment-resistant Major Depressive Disorder and Bipolar Depression. Ketamine treatment is used for hard-to-treat depression, post-traumatic stress disorder (PTSD) and other psychiatric disorders. These disorders are accompanied by abnormal brain activity with emotional alteration. Ketamine has widespread effects on brain activity of individuals who are resistant to other treatments for psychiatric disorders such as anxiety, PTSD and depression (Blanke, 2009; Iadarola, 2016).

Electroencephalogram (EEG) is a test used to record electrical activity in the brain. Brain cells communicate utilizing electrical impulses. The EEG uses electrodes on the scalp to measure the brain wave patterns and records them. The EEG is a safe procedure having been used for many years, causing no discomfort to the participant. The electrodes record brain activity but do not produce any sensation and there is minimal risk of getting an electric shock as there is no current being directly delivered to the participant. EEG has high temporal specificity with an ability to pinpoint the exact source, making it an excellent tool for this clinical study (Hubbard, 2019).

Conventionally, a wet electrode EEG system is utilized. Wet electrodes rely on conductive gel to record the brain waves. They are messier to use and require a trained EEG technician for application. Dry electrode EEG systems have up to 20 conductive pins per electrode and the pins are coated with either silver, gold or nickel. The dry electrodes do not need any gel application which makes it easier to apply and do not require as much training. This study proposes to utilize Zeto EEG system, a dry, wireless system.

Previous research has linked prefrontal EEG patterns to Ketamine effects in patients with diagnosed treatment-resistant depression (Cao, 2019). Genetic markers may play a role in the brain reactions to Ketamine. Several EEG parameters are potential endophenotypes when looking at different psychiatric disorders (Malone 2014). Researchers utilized cheek swabs to assess which markers contributed most to a decrease in absolute HAM-D scores and determined the 'Met/Met' variant of the COMT gene was the best genetic predictor of treatment outcome (Spronk 2010).

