There are inter-individual genetic variations to psychedelic drug effects. Testing for specific genetic markers helps determine the effects expected. This study will look at the following five genetic markers:

- HTR2A
- CYP2B6 gene
- C4A and C4B genes
- NRG1 gene
- DISC1 gene

This observational study will observe genetic markers and EEG patterns from pre, during and post Ketamine administration.

2. Objectives and Purpose

The objective of this observational study is to determine the effects of routine, intramuscular, clinically administered Ketamine on the brain's electrical activity and biomarkers. The brain activity will be measured with an EEG electrode cap and the biomarkers will be collected via a cheek swab.

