5.2 Exclusion Criteria

1. Pregnancy
2. Traumatic Brain Injury within past 3 months
3. Body weight < 50 kg or > 120 kg
4. Coronary heart disease
5. Uncontrolled hypertension as defined in the ACC/AHA Hypertension Guidelines
6. Previous contact with Ketamine (therapeutically or recreationally) outside of treatment at the study site
7. Primary psychotic disorder (e.g., schizophrenia, schizoaffective disorder)
8. Bipolar disorder with current manic, hypomanic or mixed state
9. Post-traumatic stress disorder
10. Obsessive-compulsive disorder
11. Primary substance-use disorder
12. Alcohol consumption 24 hours prior and 48 hours subsequent to treatment
13. Currently using any of the following medications:
 - Benzodiazepines for 6 hours prior to treatment and 2 hours after treatment
 - Lamotrigine for 6 hours prior to treatment
 - Amphetamine-based stimulants for 6 hours prior to treatment
 - MAO-Is may be taken but blood pressure must be monitored

6. Study Procedures

	Screen V1	V2	V3-V11	V12
	Day 0	Day 1 (±1 day) Session 1	Days 3, 5, 8, 11, 18, 25, 32, 46, 67 (±2 days) Sessions 2-10	Day 74 ± 2 days
Eligibility criteria	X			
Informed Consent	X			
Medical History and current medical conditions	X			
Urine HCG Pregnancy Test	X			
Demography	X			
Cheek Swab ¹		X		
Questionnaires ² (CADSS-6, QIDS-SR-16, PMQ-SF)		X	X ²	X
EEG applied ³		X	X	
EEG measured 5 ±2 min eyes closed/ 5 ±2 min eyes open prior to session		X	X	X
Wavepaths music track played		X	X	
EEG recording prior to injection and through to 15 minutes after end of session ³		X	X	
Ketamine Injection (SOC) ⁴		X	X	
Adverse Events		X	X	X
Concomitant Medications	X	X	X	X

¹ Cheek swab for testing of genetic markers and questionnaires are done directly prior to the first session beginning.

² Questionnaires to be administered at first and last sessions as well as at day 74 only for a total of 3 times each

³Sessions are approximately 60 minutes in duration, EEG is continuous for approximately 75 minutes. A digital video recording will be collected at each visit for safety monitoring.

⁴ There are a total of 10 sessions per participant over a span of 67 days

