10.3 Outcome Measures

The Primary Outcome Measure is the inter and intra patient variability in neurological activity.

The Secondary Outcomes are:

1. Correlation of neurological phenotypes with genetic markers
2. Correlation of neurological phenotypes of Clinician Administered Dissociative Symptom Scale (CADSS-6).
3. Correlation of neurological phenotypes of depressed patients with Quick Inventory of Depressive Symptomatology (QIDS SR-16)

4. Correlation of neurological phenotypes Psychedelic Music Questionnaire Short Form (PMQ-SF)

11. Administrative Procedures and Ethical Considerations

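### Section 10.2 classes cheek-swab genetic results as quantitative variables with no coding declared, so the planned summary does not show how many of the 36 participants carry each genotype

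*Combined protocol and SAP*

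**What the plan says.** Section 10.2 (Data Analysis) is a single sentence. It assigns "description statistics (mean, median, standard deviation, minimum, maximum") to "quantitative variables (e.g., cheek swabs, EEG data"), and it assigns "counts and percentages for categorical variables (e.g., gender"). Cheek swabs are therefore named on the quantitative side.

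Other parts of the protocol describe what the swab yields:

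- Footnote 1 to the schedule table in section 6: "Cheek swab for testing of genetic markers".
- End of section 1.2: "This study will look at the following five genetic markers". The list is HTR2A, CYP2B6, C4A and C4B, NRG1 and DISC1.
- Glossary entry for DISC1: "Disrupted in Schizophrenia 1 genotype".
- Section 1.2, on earlier work with swabs: the Met/Met "variant of the COMT gene was the best genetic predictor of treatment outcome".

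The markers have two roles. Section 2.1 makes them candidate predictors of treatment response, alongside baseline EEG measures. Secondary outcome 1 in section 10.3 is "Correlation of neurological phenotypes with genetic markers". The text available for this review names genes but gives no variant, numeric coding, genotype grouping or allele frequency, and nothing in it corrects the classification in 10.2.

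**The concern.** A genotype is a category unless a coding rule turns it into a number. Section 10.2 applies the summary for numbers without giving such a rule. A statistician following the sentence literally would have to invent codes, and the resulting table would describe those codes as much as the participants.

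The table would also leave out what a reader needs most. In a study of 36 people that section 10.1 describes as determining the feasibility of these measurements, the basic genetic result is how many participants fall in each genotype group. That number determines whether any comparison or correlation involving the marker can be informative. If coding is left open until the data are seen, it can also be chosen with the results in view.

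**Working it through.** **Inputs.** N = 36 comes from section 10.1. The summary statistics and the quantitative/categorical split come from section 10.2. There is no plan figure to reproduce: 36 is justified by unquantified precision for EEG comparisons, and this point does not dispute it. Genotype splits and allele frequencies below are illustrative assumptions.

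**Step 1: do the passages agree?** Section 10.2 treats the swab result as a quantity. The section 6 footnote calls it a test of genetic markers, the glossary calls DISC1 a genotype, and section 1.2 cites a named gene variant as a predictor. No passage describes a continuous read-out. The classification in 10.2 does not fit the rest of the document.

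**Step 2: does the summary depend on the coding?** Take 25 common homozygotes, 10 heterozygotes and 1 rare homozygote. The mean is (25a + 10b + 1c)/36 for codes a, b, c.

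| Codes (a, b, c) | Mean | SD | Median | Min, max |
|---|---|---|---|---|
| 0, 1, 2 | 12/36 = 0.33 | 0.53 | 0 | 0, 2 |
| 0, 2, 1 | 21/36 = 0.58 | 0.91 | 0 | 0, 2 |
| 1, 0, 2 | 27/36 = 0.75 | 0.50 | 1 | 0, 2 |
| 1, 2, 0 | 45/36 = 1.25 | 0.50 | 1 | 0, 2 |
| 2, 0, 1 | 51/36 = 1.42 | 0.91 | 2 | 0, 2 |
| 2, 1, 0 | 60/36 = 1.67 | 0.53 | 2 | 0, 2 |

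The same 36 people give six different means, three different SDs and three different medians. Minimum and maximum never change.

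**Step 3: does a sensible coding make the group sizes visible?** Code each person by number of minor alleles (0, 1, 2) and consider three splits of 36:

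- 26/7/3: mean 13/36 = 0.361, SD 0.639
- 24/10/2: mean 14/36 = 0.389, SD 0.599
- 21/14/1: mean 16/36 = 0.444, SD 0.558

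At one decimal, all three print as mean 0.4, SD 0.6, median 0, range 0 to 2. A rare group of 1 cannot be told from a rare group of 3. Unrounded, no two splits of 36 share both mean and SD, so the counts could be worked back, but the table would not show them.

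**Step 4: how small might the groups be?** Assume one biallelic variant in Hardy-Weinberg proportions with minor-allele frequency q. Expected counts are 36(1−q)², 72q(1−q) and 36q². The chance of no rare homozygote is (1−q²)^36.

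| q | Common homozygote | Heterozygote | Rare homozygote | P(no rare homozygote) |
|---|---|---|---|---|
| 0.10 | 29.2 | 6.5 | 0.4 | 70% |
| 0.20 | 23.0 | 11.5 | 1.4 | 23% |
| 0.30 | 17.6 | 15.1 | 3.2 | 3% |
| 0.50 | 9.0 | 18.0 | 9.0 | about 0% |

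These are expectations, not bounds. At q = 0.30 the rare group follows a binomial distribution with n = 36 and probability 0.09. The chance of 3 or fewer is about 59%, so 4 or more occur about 41% of the time.

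**The case against.** The best defence is that this is a drafting slip in an illustrative list. Section 10.2 introduces its examples with e.g., and it already provides counts and percentages for categorical variables, so no new method is needed. That is fair as to how small the correction is. It does not remove the problem, because cheek swabs are named explicitly and the available text says nothing different elsewhere.

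The defence is stronger against four readings that go further.

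- A reader might infer that the mean of a genotype can never have meaning. Under a declared minor-allele count, half the mean is the allele frequency. The defect is that no coding is declared.
- A reader might infer that the plan conceals near-empty genotype groups. The documents give no allele frequencies, and step 4 shows 9 expected rare homozygotes at q = 0.50. Section 10.2 also plans no three-group comparison.
- A reader might infer that arbitrary codes will pass into the section 10.3 correlations. Section 10.2 covers descriptive summaries, and 10.3 gives neither a method nor a coding. The link is possible but not stated.
- A reader might infer that every swab result must be categorical, with particular classes or a minimum group size. The available text names genes without read-outs, and part of the glossary was not available for this review. A numeric read-out for some marker cannot be ruled out, and for such a marker a quantitative summary could be acceptable.

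The stakes also have a limit. Genetic markers are in the primary objective, but the primary outcome in 10.3 is variability in neurological activity. Among the listed outcomes, genetics appears only as secondary outcome 1.

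**Conclusion.** The point holds in a limited form. Section 10.2 puts genetic test results on the quantitative side, contrary to how the protocol describes them elsewhere. Followed as written, it gives a summary that depends on undeclared codes and does not show the number of participants per genotype. That conclusion rests on the text and on simple arithmetic, and needs no assumption about allele frequency.

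Sparse genotype groups are a conditional concern only: likely under the step 4 assumptions if the minor allele is uncommon, unlikely if it is near 0.50. Carry-over into the correlations is a risk to close off, not something the plan says. The error affects descriptive reporting. It does not bear on N = 36, and the individual genotypes would still be available for correct tabulation.

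**What to change.** In section 10.2, move genotype results to the categorical list and report, for each marker, the count and percentage of participants with each genotype. Keep a quantitative summary only for a marker whose read-out is truly numeric. To apply this, state the variable type marker by marker.

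For secondary outcome 1 in section 10.3, state each marker's coding before the data are examined, for example the number of minor alleles.

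The cost is a short edit and the matching table shells. Someone must confirm with the genetics laboratory what is reported for each marker. Sample size, visits and procedures do not change.

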10.3 Outcome Measures

The Primary Outcome Measure is the inter and intra patient variability in neurological activity.

The Secondary Outcomes are:

1. Correlation of neurological phenotypes with genetic markers
2. Correlation of neurological phenotypes of Clinician Administered Dissociative Symptom Scale (CADSS-6).
3. Correlation of neurological phenotypes of depressed patients with Quick Inventory of Depressive Symptomatology (QIDS SR-16)

4. Correlation of neurological phenotypes Psychedelic Music Questionnaire Short Form (PMQ-SF)

11. Administrative Procedures and Ethical Considerations

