1.1 Rationale

This observational study will allow data to be collected to demonstrate changes in brain activity following administration of standard of care (SOC) Ketamine. By comparing genetic markers across participants, data on impact of genetic markers and response to Ketamine will also be analysed. This data will contribute to the design of future studies utilizing Ketamine for various psychiatric disorders. This study will focus on treatment-resistant Major Depressive Disorder (MDD).

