2.1 Primary Objective

The primary objective is to study what baseline EEG measures and genetic markers predict a Ketamine treatment response among participants with treatment-resistant Major Depressive Disorder.

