2.2 Secondary Objectives

The secondary objectives are to:

- Evaluate neurological changes during Ketamine sessions via EEG
- Evaluate persistent neurological changes in a follow up session post-treatment
- Identify biomarkers based on neurological changes during Ketamine sessions via cheek swab

3. Study Description

This is an Open Label Observational Study with the primary objective to assess brain activity in patients prior to, during and after Ketamine treatment and to assess genetic markers prior to Ketamine treatment. This is a non-interventional study that will observe the EEG pattern of participants who, per standard of care, are treated with intramuscular Ketamine. The administration of the Ketamine during this study is not considered investigational. The experimental intervention, measurements via EEG, will be offered to patients of the study

site presenting for intramuscular (IM) ketamine treatment per the site's established and evidence-based protocol as part of their regular clinical care. Participants in this study have already been determined to have a medically appropriate indication for IM Ketamine treatment, independent of enrollment in this study. Given the requirement, per study protocol, to wear an EEG headset, permit a video recording of the session and complete study measures, participants will be compensated by having treatment costs paid by the study sponsor.

There will be 36 participants enrolled.

4. Scheduling of Visits

All visits will occur at the clinic of the principal site investigator. The study will enrol for approximately 3-4 months. All times should be recorded using the 24-hour clock.

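### The primary objective in 2.1, predicting Ketamine response from baseline EEG and genetic markers, has no matching primary outcome, no analysis and no definition of response

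*Combined protocol and SAP*

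**What the plan says.** Section 2.1: "The primary objective is to study what baseline EEG measures and genetic markers predict a Ketamine treatment response". Section 1.1 makes a matching promise: "data on impact of genetic markers and response to Ketamine will also be analysed". The markers are introduced in 1.2 with "This study will look at the following five genetic markers"; the list under that sentence has five entries but names six genes, because C4A and C4B share one entry.

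Section 10.3 gives the primary outcome: "The Primary Outcome Measure is the inter and intra patient variability in neurological activity". It adds four secondary outcomes, which correlate EEG phenotypes with genetic markers, CADSS-6, QIDS-SR-16 and PMQ-SF in turn.

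The analysis in 10.2 reads "The information will be summarized using description statistics (mean, median, standard deviation, minimum, maximum" for quantitative variables, with counts and percentages for categorical ones. Cheek swabs are given there as an example of a quantitative variable.

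Section 3 words the primary objective differently: "primary objective to assess brain activity in patients prior to, during and after Ketamine treatment and to assess genetic markers prior to Ketamine treatment". Section 10.1 adds: "This is an open-label, observational study to determine the feasibility of these measurements".

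**The concern.** A primary objective about prediction needs three things: a defined response, a defined set of predictors, and an estimate linking the two. Here the primary outcome supplies none of them, and the analysis section has no measure of association.

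Two things are at stake. If 2.1 is meant, the study can finish as planned without answering its main question, although the swab, the baseline EEG and QIDS-SR-16 are all scheduled. A response analysis added afterwards would be free to choose the scale, the time point (Day 67 or Day 74) and the EEG feature after the data had been seen. If only description and feasibility are meant, 2.1 and 1.1 promise a result the study is not set up to give.

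**Working it through.** The check is mainly a comparison of sections.

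**Step 1. What each section treats as primary or plans to analyse.**

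| Section | Content | Response? | Genotype? |
|---|---|---|---|
| 2 (opening) | Effects of Ketamine on brain electrical activity and biomarkers | No clinical response | As a biomarker |
| 2.1 | Prediction of response from baseline EEG and markers | Yes, undefined | Yes, as predictor |
| 3 | Brain activity before, during and after treatment; markers before | No | Assessed only |
| 10.1 | Baseline brain activity and markers, then in-session change; feasibility | No | Assessed only |
| 10.2 | Descriptive summaries | No | Summarised; coding not set |
| 10.3, primary | Between- and within-patient EEG variability | No | No |

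Only 2.1 contains prediction. Sections 2, 3, 10.1 and 10.3 also differ among themselves.

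**Step 2. Is response defined anywhere?** MADRS appears only as an eligibility threshold (5.1). QIDS-SR-16 is scheduled at Session 1, Session 10 (Day 67) and Day 74, but is never called the response measure. No change score, cut-off or time point is given.

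**Step 3. Do the secondary outcomes fill the gap?** It depends on what response means.

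- Clinical response: outcome 3 (EEG with QIDS-SR-16) is nearest, but does not specify baseline EEG, change in score or time point. No outcome relates genotype to clinical response.
- Brain response, as 1.2 might suggest ("Genetic markers may play a role in the brain reactions to Ketamine"): outcome 1 (EEG with genes) covers genotype, but only as a secondary outcome.

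On either reading the primary outcome does not address 2.1, and 10.2 gives no method for any of the four correlations.

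**Step 4. Sample size.** The figure of 36 cannot be reproduced. Section 10.1 gives no alpha, power, effect size, SD or precision target, and refers to comparing EEG over time, not to prediction.

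**Step 5. Illustration of what 36 could show.** Assumptions, none from the documents: one continuous marker against a continuous response, all 36 evaluable, two-sided alpha 0.05, 80% power, Fisher z.

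- Detectable r = tanh((z for alpha + 0.842) / sqrt(n − 3)), with sqrt(33) = 5.745.
- One marker: tanh((1.960 + 0.842) / 5.745) = tanh(0.488) = 0.45.
- Five markers, Bonferroni alpha 0.01: tanh((2.576 + 0.842) / 5.745) = tanh(0.595) = 0.53.
- One marker with fewer evaluable: 0.49 at n = 30 and 0.53 at n = 25 (0.535 before rounding).
- Precision: an observed r of 0.30 at n = 36 has a 95% CI of tanh(0.310 ± 1.960 / 5.745), that is −0.03 to 0.57.

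These are simple correlations. They should not be set beside partial correlations from a model that adjusts for the Session 1 score, because the two are on different scales and adjustment need not cost power.

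**The case against.** The strongest reply is that this is an uncontrolled observational study which 10.1 describes as one of feasibility, that a correlation coefficient is compatible with a descriptive analysis, and that 10.3 already names correlations of EEG with genes and with depression score. The opening of section 2 and the third secondary objective in 2.2 also lean towards a brain-response reading, under which the genetic part of 2.1 is partly covered.

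Much of this stands. A reader might infer that the plan would report nothing linking EEG to genes or symptoms; the documents do not support that, because the four correlations are named. What remains is that they are secondary, underspecified and absent from 10.2. A feasibility aim does not rescue a primary objective that asks for prediction; it is a reason to reword that objective.

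Three other inferences go too far.

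- **The last session is undefined.** The schedule, its footnotes and 6.6 place Session 10 on Day 67 and list Day 74 separately, giving three questionnaire occasions. Only the count of two in 6.1 and the Session 11 label in 6.7 disagree.
- **The plan carries an inflated false-positive rate.** It proposes no significance tests, so any such rate belongs to a hypothetical later analysis.
- **The study is underpowered.** The documents give no target effect to judge that against.

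**Conclusion.** The point holds. As written, the plan does not estimate the objective it calls primary: the primary outcome contains neither response nor genotype, the analysis is descriptive, and response is undefined. This is more than missing detail, because sections 2, 2.1, 3, 10.1 and 10.3 point to different primary questions. It should be settled before outcome data are examined.

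The conclusion does not depend on which meaning of response is intended, nor on any calculation. The detectable correlations of about 0.45 and 0.53 rest on assumed alpha, power and full follow-up, and show only that a prediction analysis at this size would be exploratory. One limit applies: front pages were not available for review, so a definition of response placed there cannot be excluded.

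**What to change.** The sponsor chooses the route.

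**Route A, if 2.1 stands.**

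- In 10.3, name QIDS-SR-16 at one fixed time point as the response outcome for 2.1. Day 74 is one option, being the only occasion scheduled after all ten sessions. Keep EEG variability as a separate descriptive outcome, and align 2, 3 and 10.1 with this.
- In 10.2, fix the genotype coding and a short list of baseline EEG features before outcome data are examined. For each marker or feature, regress the chosen score on the Session 1 QIDS-SR-16 and that marker or feature.
- Report 95% CIs, with multiplicity-adjusted p-values if any are given. Label the results exploratory and state the number of missing scores. Multiple imputation is optional.
- Inclusion 3 and exclusion 6 together admit people already treated with Ketamine at the site, so Session 1 may not be a pre-treatment baseline for everyone. Record prior on-site treatment and either add it as a covariate or repeat the analysis without those participants. Section 6.3 does not clearly say that past Ketamine is captured, so this may need site records or one CRF field.

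**Route B, if only description and feasibility are intended.** State one common primary objective across 1.1, 2, 2.1, 3, 10.1 and 10.3. Make no claim about predictors of response. Add the four 10.3 correlations to 10.2 as descriptive estimates with CIs. Rewording 1.1 and 2.1 alone is not enough, because the remaining sections disagree with one another.

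**Either route.** Bring the questionnaire count in 6.1 and the session label in 6.7 into agreement with the schedule (three questionnaire occasions, ten sessions), so that the chosen time point is collected.

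**Cost.** Both routes need an amendment with IRB approval, but no extra patients or visits. Route A adds one model per marker or feature, possibly a CRF field, and wide intervals. Route B is wording plus CIs for the correlations, and gives up the prediction claim.

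### The gene–EEG outcome does not define the EEG phenotype or use the same-session pre-dose EEG, so a marker of resting EEG could be read as a marker of in-session change

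*Combined protocol and SAP*

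**What the plan says.** Three parts of the protocol bear on this point.

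- **Objective.** The third secondary objective (Section 2.2) is to "Identify biomarkers based on neurological changes during Ketamine sessions via cheek swab". It asks about change during sessions.
- **Outcome and analysis.** The only outcome that links genes to EEG is item 1 of the secondary outcomes in Section 10.3: "Correlation of neurological phenotypes with genetic markers". The protocol does not say whether the phenotype is a resting level, an in-session level or a change. It also does not say which time window applies or how 10 sessions per participant are combined. Section 10.2 adds only that "The information will be summarized using description statistics"; it names no model, covariate or change score.
- **Data available.** The schedule in Section 6 includes "EEG measured 5 ±2 min eyes closed/ 5 ±2 min eyes open prior to session", and Sections 6.4 to 6.6 place this recording before the injection at every one of Sessions 1 to 10.

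Two other statements give context. Section 1.2 says that "Several EEG parameters are potential endophenotypes when looking at different psychiatric disorders", and the glossary describes an endophenotype as a reasonably heritable trait. The primary objective (Section 2.1) asks "what baseline EEG measures and genetic markers predict a Ketamine treatment response", so resting EEG also has a role of its own as a predictor.

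**The concern.** On the protocol's own premise, some markers may be related to a person's resting EEG whatever Ketamine does. If EEG during the session carries part of that resting level forward, correlating in-session EEG with a marker mixes two things: the level the person arrived with, and the shift during the session that Section 2.2 asks about. The recording that would separate them is collected at every session, but the plan does not say that it will be used.

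Two consequences follow if in-session levels are analysed without it. A marker of resting EEG may be reported as a marker of the in-session response. A real marker effect is also estimated less precisely, because variation in resting level stays in the residual. Section 1.1 says the data will feed into the design of later studies, so a mislabelled marker would be carried forward.

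**Working it through.** **Inputs from the protocol.** N = 36 (Sections 3 and 10.1), 10 sessions, and pre-dose EEG at each session. Section 10.1 gives no effect size, SD, alpha, power or interval width, only that 36 participants "should have the precision needed to observe and compare EEG activity pre, during and post Ketamine administration". The sample size therefore cannot be reproduced. For scale, the 95% Fisher interval around an observed correlation of 0 at n = 36 is tanh(±1.96/√33) = ±0.33.

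**Assumed inputs, none stated in the protocol.** A two-group marker split 18/18; two-sided 5% tests; correlation ρ between resting and in-session EEG of 0.3, 0.5 or 0.7; a marker difference of 0.8 SD (alternatively 0.5 SD) in resting EEG; a true marker effect of 0.8 SD on in-session EEG for the power calculation. There is one resting and one in-session value per participant, so these figures do not model the 10 repeated sessions.

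**Model.** Resting EEG x = b·g + e. In-session EEG y = ρ·x + √(1−ρ²)·e₂ + d·g. Here g is the marker group (0 or 1), and e and e₂ have SD 1. The SD of y within a marker group is then √(ρ² + 1 − ρ²) = 1.

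**Step 1: marker related to resting EEG only (d = 0).** The groups differ in y by ρ·b. With 18 per group the noncentrality of the unadjusted t-test is ρ·b/√(2/18) = 3ρb. For b = 0.8 this is 0.72, 1.20 and 1.68. The t-test with 34 df is then significant with probability 10.8%, 21.5% and 37.2%. Simulation of 6,000 trials per scenario gave:

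| ρ | unadjusted, b = 0.8 | unadjusted, b = 0.5 | adjusted for x |
|---|---|---|---|
| 0.3 | 10.7% | 7.6% | about 5% |
| 0.5 | 21.8% | 11.2% | about 5% |
| 0.7 | 37.0% | 17.6% | about 5% |

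**Step 2: power for a true effect (d = 0.8, b = 0).** Adjustment multiplies the residual variance by 1 − ρ², a cut of ρ² = 9%, 25% and 49%. Simulated power:

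| ρ | unadjusted | adjusted | gain in points |
|---|---|---|---|
| 0.3 | 64.7% | 67.5% | 2.8 |
| 0.5 | 65.5% | 76.3% | 10.8 |
| 0.7 | 64.5% | 89.3% | 24.8 |

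The normal-approximation formula agrees in pattern: 67% unadjusted, and 71%, 79% and 92% adjusted.

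**Step 3: noisy pre-dose EEG.** With reliability 0.8 and b = 0.8, the adjusted rate was about 5%, 6% and 7%, against 10%, 22% and 38% unadjusted. In a wider grid (ρ up to 0.9, marker–resting correlation up to 0.5) the adjusted rate reached 17%, in a setting where the unadjusted rate was 83%.

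**Step 4: change score instead.** If in-session EEG moves one-for-one with resting EEG, testing the change from pre-dose already gives about 5%. If the slope is below 1, the change score is significant in 7% to 43% of trials over the same grid with error-free pre-dose EEG. Those are not simply errors. In the Step 1 model the marker does shift y − x, by (ρ − 1)·0.8 = −0.56, −0.40 and −0.24 SD. The marker is null only conditional on resting EEG, so change and adjusted level answer different questions.

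**The case against.** The strongest objection is that the protocol never says the phenotype is a raw in-session level. A reader might infer from Section 10.3 that the plan commits to an unadjusted in-session correlation and will therefore mislabel resting-EEG markers. The documents do not support that: the term is undefined, Section 2.2 speaks of changes, and Section 10.1 speaks of comparing EEG before, during and after dosing. If the phenotype were a change score, the problem could be absent or take another form (Step 4). If it were resting EEG itself, adjusting for resting EEG would remove the association of interest. This objection stands, and it makes the point conditional.

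Other limits also stand.

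- No test, alpha or power is planned, and Section 10.1 describes a feasibility aim. The rates illustrate the risk; they are not operating characteristics of a stated test.
- The 5% after adjustment assumes that pre-dose EEG is measured without error.
- From Session 2 on, the pre-dose EEG follows earlier doses, nominally by as little as two days (Day 1 to Day 3). Section 2.2 treats persistent change as of interest in itself, and same-session adjustment may absorb part of a marker effect on it.
- Inclusion criterion 3 admits people already receiving Ketamine, and exclusion criterion 6 allows earlier exposure at the study site. Session 1 resting EEG is therefore not necessarily drug-free.
- Music starts between the resting recording and the injection (Section 6.2), so adjustment does not isolate a Ketamine effect.

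None of this supplies the missing definition. The outcome as worded allows the unadjusted in-session analysis, and nothing in Section 10 excludes it.

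**Conclusion.** The concern holds in conditional form. Secondary outcome 1 leaves the phenotype undefined and states no use of the same-session pre-dose EEG, although the objective it serves is about change during sessions. If in-session levels are used, a marker related only to resting EEG appears as a marker of the in-session response in about 11%, 22% and 37% of trials at ρ = 0.3, 0.5 and 0.7, against about 5% after adjustment, or somewhat more with a noisy pre-dose recording. The power gain for a true effect is about 3, 11 and 25 points.

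Every one of these figures rests on assumed inputs: ρ, the 18/18 split, the 0.8 SD differences and the 5% level. With a 0.5 SD resting difference the unadjusted rates fall to about 8%, 11% and 18%, and at ρ = 0.3 the gain in power is small. It would go too far to say that the plan produces false Ketamine markers, or that a marker acting through resting EEG has no effect on change. The first depends on an undefined phenotype. The second is true only conditional on resting EEG.

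**What to change.** In Section 10.3, item 1, for the third objective of Section 2.2:

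1. Define the phenotype as in-session EEG, naming the feature and time window.
2. Replace the plain correlation with a regression of in-session EEG on the marker, with the same feature's pre-dose EEG from the same session as covariate and a participant random effect across the 10 sessions. Report the marker coefficient with its 95% CI, described as an association conditional on pre-dose EEG.
3. Add two sensitivity analyses: change from pre-dose; and Session 1 only, or Session 1 pre-dose EEG as the covariate throughout. The second is needed because later pre-dose recordings may already carry persistent Ketamine effects.
4. Report the association of each marker with Session 1 resting EEG separately, labelled as resting EEG at study entry and not as a drug-free trait.
5. Describe the result as in-session change and not as a pure Ketamine effect, because the music starts after the resting recording.

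The cost is a wording change, one degree of freedom for the covariate and a little more analysis. No new visits, data or participants are needed. If resting and in-session EEG turn out to be weakly correlated, the adjustment will gain little power.
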